9 CLINICAL DATA HANDLING

The Sponsor will be responsible for the data handling. The Sponsor and/or its affiliates will be responsible for compiling and submitting all required reports to governmental agencies. Data will

This confidential document is the property of Abbott and shall not be reproduced, distributed, disclosed or used without the express written consent of Abbott.

be analyzed by the Sponsor and may be transferred to the Sponsor's locations worldwide and/or any other worldwide regulatory authority in support of a market-approval application.

9.1 PROTECTION OF PERSONALLY IDENTIFIABLE INFORMATION

Abbott respects and protects personally identifiable information collected or maintained for this clinical investigation. The privacy of each subject and confidentiality of his/her information will be preserved in reports and when publishing any data. Confidentiality of data will be observed by all parties involved at all times throughout the clinical investigation. All data will be secured against unauthorized access. It is the responsibility of the investigational site to ensure the removal of subject identifiers and to add the substitution of the patients ID number

9.2 DATA MANAGEMENT PLAN

A Data Management Plan (DMP) will describe procedures used for data review, database cleaning, and issuing and resolving data queries. If appropriate, the DMP may be updated throughout the clinical investigation duration. All revisions will be tracked and document controlled.

Subject data will be captured in a validated electronic data capture (EDC) system hosted by the Sponsor.

Only authorized site personnel will be permitted to enter the CRF data through the EDC system deployed by Abbott. An electronic audit trail will be used to track any subsequent changes of the entered data.

9.3 DOCUMENT AND DATA CONTROL

9.3.1 Traceability of Documents and Data

The investigator will ensure accuracy, completeness legibility and timeliness of the data reported to the Sponsor on the CRFs and in all required reports.

9.3.2 Recording Data

The CRF will be reviewed by the authorized site personnel. An appropriate comment will be provided to explain changes to data reported on the CRF.

10 DATA MONITORING

It is the responsibility of the Sponsor to ensure the clinical investigation is conducted, recorded and reported according to the approved CIP, subsequent amendment(s), applicable regulations and guidance documents.

Prior to beginning the clinical investigation, the Sponsor will contact the investigator or designee to train on the clinical investigational plan and the data collection requirements. Abbott personnel will remotely review the subject data and appropriate associated source documents and issue queries as appropriate.

11 COMPLIANCE STATEMENT

11.1 STATEMENT OF COMPLIANCE

In addition to applicable regional or local laws and regulations, this clinical investigation will be conducted in compliance with the most current version of the World Medical Association (WMA) Declaration of Helsinki and 21 CFR Parts 50, 54, 56 and 812. In the event of any conflicts, local laws and regulations will have precedence and in such cases, good faith efforts will be made to adhere to the intent of the other documents.

This confidential document is the property of Abbott and shall not be reproduced, distributed, disclosed or used without the express written consent of Abbott.

The investigator will sign a Clinical Trial Agreement and agrees to be compliant with it. The investigator will not start enrolling subjects or requesting informed consent from any subject prior to obtaining IRB/EC approval and relevant Regulatory Authority approval, if applicable, and authorization from the Sponsor in writing for the clinical investigation. If additional requirements are imposed by the IRB, those requirements will be followed. If any action is taken by an IRB with respect to the clinical investigation, that information will be forwarded to the Sponsor.

11.2 QUALITY ASSURANCE AUDITS AND REGULATORY INSPECTIONS

The investigator and/or delegate should contact the Sponsor immediately upon notification of a regulatory authority inspection at the site. A monitor or designee will assist the investigator and/or delegate in preparing for the audit. The Sponsor may perform quality assurance audits, as required.

The Principal Investigator or institution will provide direct access to source data during and after the clinical investigation for monitoring, audits, IRB/ review and regulatory authority inspections, as required. The Principal Investigator or institution will obtain permission for direct access to source documents from the subject, hospital administration and national regulatory authorities before starting the clinical investigation.

11.3 REPEATED AND SERIOUS Non-COMPLIANCE

In the event of repeated non-compliance or a one-time serious non-compliance, as determined by the Sponsor, a monitor or designee will attempt to secure compliance by one or more of the following actions:

- Visiting the investigator,
- Contacting the investigator by telephone,
- Contacting the investigator in writing,
- Retraining of the investigator.

If an investigator is found to be repeatedly non-compliant with the signed agreement, the CIP or any other conditions of the clinical investigation, the Sponsor will either secure compliance or, at its sole discretion, terminate the investigator's participation in the clinical investigation. In case of termination, the Sponsor will inform the responsible regulatory authority, as required, and ensure that the IRB is notified, either by the Principal Investigator or by the Sponsor.

12 SUSPENSION OR PREMATURE TERMINATION OF THE CLINICAL INVESTIGATION

The Sponsor reserves the right to terminate the clinical investigation at any stage, with appropriate written notice to the investigators, and IRB, if required.

A Principal Investigator, IRB or regulatory authority may suspend or prematurely terminate participation in a clinical investigation at the investigational sites for which they are responsible. The investigators will follow the requirements specified in the Clinical Trial Agreement.

If suspicion of an unacceptable risk to subjects arises during the clinical investigation or when so instructed by the IRB or regulatory authority, the Sponsor may suspend the clinical investigation while the risk is assessed. The Sponsor will terminate the clinical investigation if an unacceptable risk is confirmed. If the Sponsor completes an analysis of the reasons for the suspension, implements the necessary corrective actions, and decides to lift the temporary suspension, the Sponsor will inform the Principal Investigators, IRB, or regulatory authority, where appropriate, of the rationale, providing them with the relevant data supporting this decision. Approval from the IRB/EC or regulatory authority, where appropriate, will be obtained before the clinical

investigation resumes. If subjects have been informed of the suspension, the Principal Investigator, or authorized designee will inform them of the reasons for resumption.

If the Sponsor suspends or prematurely terminates the clinical investigation at an individual investigational site in the interest of safety, the Sponsor will inform all other Principal Investigators.

If suspension or premature termination occurs, the Sponsor will remain responsible for providing resources to fulfill the obligations from the CIP and existing agreements for following up the subjects enrolled in the clinical investigation, and the Principal Investigator or authorized designee will promptly inform the enrolled subjects at his/her investigational site, if appropriate.

13 CLINICAL INVESTIGATION CONCLUSION

The clinical investigation will be concluded when:

- All sites are closed AND
- The study is closed with the approving IRB.

14 PUBLICATION POLICY

Publications or presentations of clinical investigation methods or results will adhere to Abbott's publication policy, which is based on Good Publication Practices and International Committee of Medical Journal Editors (ICMJE) guidelines. A copy of the policy will be provided upon request of the investigator. Publication planning and authorship determinations will be overseen by the Steering Committee (see section 5.14), and investigators will be notified via email about the dissemination of study data and opportunities for involvement as authors on publications/presentations.

15 REPORTING RESULTS ON CLINICALTRIALS.GOV WEBSITE

This feasibility clinical investigation will be registered on ClinicalTrials.gov. as per the requirements.

Appendix A: CIP Revisions

Procedure for CIP Amendments

This CIP may be amended as appropriate by the Sponsor. Rationale will be included with each amended version in the revision history table below. The version number and date of amendments will be documented.

CIP Amendments will be acknowledged by the Principal Investigators will be collected on the signature pages.

IRB/EC and relevant Regulatory Authorities, if applicable, will be notified of amendments to the CIP.

Table 3 – CIP Revision History

Amendment Number	Version	Date	Rationale	Details
Not Applicable	A	4/28/2017	First release of CIP	NA
1	B	6/15/2018	Changes to exclusion criteria and clarification of safety and death reporting timeframe	Changed exclusion criteria to allow for enrollment of MOMENTUM 3 CAP patients. Changed safety and death reporting timeframe to 3 calendar days.

Appendix B: Definitions

Non-study Specific Definitions

Adverse Event (AE)

Any untoward medical occurrence, unintended disease or injury, or untoward clinical signs (including abnormal laboratory findings) in subjects, users or other persons, whether or not related to the study medical device under clinical investigation.

Serious Adverse Event (SAE)

An SAE is any untoward medical occurrence which resulted in serious injury to a subject or other person. A serious adverse event is one that led to:

- Death
- A serious deterioration in the health of the subject, that either resulted in:
 - A life-threatening illness or injury OR
 - A permanent impairment to a body structure or a body function OR
 - An in-patient or prolonged hospitalization OR
 - A medical or surgical intervention to prevent life-threatening illness or injury or permanent impairment to a body structure or a body function OR
- Fetal distress, fetal death or a congenital abnormality or birth defect

A planned hospitalization for a pre-existing condition, or a procedure required by the CIP is not considered a serious adverse event.

Adverse Device Effect (ADE)

An adverse event related to the use of the study device when the occurrence does not meet the definition of serious.

This definition includes adverse events resulting from insufficient or inadequate instructions for use, deployment, implantation, installation, or operation, or any malfunction of the investigational medical device.

This definition includes any event resulting from the use error or from intentional misuse of the investigational medical device.

Serious Adverse Device Effect (SADE) An adverse device effect that has resulted in any of the consequences characteristic of a serious adverse event.

Study Specific Definitions

Cardiac Arrhythmias

Any documented arrhythmia that results in clinical compromise (e.g., diminished VAD flow, oliguria, pre-syncope or syncope) that requires hospitalization or occurs during a hospital stay. Cardiac arrhythmias are classified as 1 of 2 types:

- 1) Sustained ventricular arrhythmia requiring defibrillation or cardioversion.
- 2) Sustained supraventricular arrhythmia requiring drug treatment or cardioversion.

Hospitalization

Defined as an admission to the hospital for greater than or equal to 24 hours.

Heart Failure (HF) Hospitalization

HF hospitalization meets the definition of hospitalization and is further determined to be related to heart failure when the diagnosis of heart failure is listed on the discharge diagnosis.

Neurologic Dysfunction

Any new, temporary or permanent, focal or global neurological deficit, ascertained by a standard neurological history and examination administered by a neurologist or other qualified physician and documented with appropriate diagnostic tests and consultation note; or an abnormality identified by surveillance neuroimaging. The examining physician will classify the event as defined below:

- a. Transient ischemic attack*, defined as an acute transient neurological deficit conforming anatomically to arterial distribution cerebral ischemia, which resolves in < 24 hours and is associated with no infarction on brain imaging (head CT performed >24 hours after symptom onset; or MRI)
- b. Ischemic Stroke*: a new acute neurologic deficit of any duration associated with acute infarction on imaging corresponding anatomically to the clinical deficit, or a clinically covert ischemic stroke seen by surveillance imaging, without clinical findings of stroke or at the time of event recognition.
- c. Hemorrhagic Stroke*: a new acute neurologic deficit attributable to intracranial hemorrhage (ICH), or a clinically covert ICH seen by surveillance imaging, without clinical findings of ICH at the time of event recognition.
- d. Encephalopathy: Acute new encephalopathy** due to hypoxic-ischemic injury (HIE), or other causes, manifest as clinically evident signs or symptoms, or subclinical electrographic seizures found by complete neurological diagnostic evaluation to be attributable to acute global or focal hypoxic, or ischemic brain injury not meeting one of ischemic stroke or ICH events as defined above.
- e. Seizure of any kind
- f. Other neurological event (non-CNS event): examples include neuro muscular dysfunction or critical care neuropathy

*Modified Rankin Score will be used to classify the severity of all strokes (See Appendix E: Modified Rankin Score)

**Acute encephalopathy is a sign or symptom of some underlying cerebral disorder, and is manifest as depressed consciousness with or without any associated new global or multifocal neurologic deficits in cranial nerve, motor, sensory, reflexes and cerebellar function.

Renal Dysfunction

Two categories of renal dysfunction will be identified:

Acute Renal Dysfunction

This confidential document is the property of Abbott and shall not be reproduced, distributed, disclosed or used without the express written consent of Abbott.

Abnormal kidney function requiring dialysis (including hemofiltration) in Subjects who did not require this procedure prior to implant, or a rise in serum creatinine of greater than 3 times baseline or greater than 5 mg/dl sustained for over 48 hours.

Chronic Renal Dysfunction

An increase in serum creatinine of 2 mg/dl or greater above baseline, or requirement for hemodialysis sustained for at least 90 days.

Right Heart Failure

Symptoms and signs of persistent right ventricular dysfunction requiring RVAD implantation, or requiring inhaled nitric oxide or inotropic therapy for a duration of more than 1 week at any time after LVAD implantation.

Syncope/Presyncope/dizziness or hypovolemia

Transient sensation that may lead to inability to maintain an upright posture. Can be felt as lightheadedness, muscular weakness, blurred vision, feeling faint and. In extreme cases could lead to fainting (syncope).

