2 BACKGROUND AND JUSTIFICATION FOR CLINICAL INVESTIGATION

Heart failure (HF) is a progressive condition which affects the heart's ability to pump blood to the body's tissues and organs. Symptoms of HF include fluid retention, dyspnea, and exercise intolerance. When patients advance to NYHA class IIIA and are hospitalized, the CardioMEMS™ HF system is indicated for wireless PA pressure monitoring to guide HF management¹. As the disease progresses to NYHA class IIIB, the HeartMate LVAD becomes an important treatment option for patients ineligible for cardiac transplant or those awaiting transplant. The pump is implanted in parallel with the native heart and is intended to provide long-term hemodynamic support^{2,3}. HeartMate use in advanced HF patients results in increased survival, quality of life, and functional status^{2,4}.

The majority of patients respond well clinically to LVAD support and improve to NYHA class I or II. However, approximately 20% of LVAD patients continue to experience poor functional status with NYHA class III or IV symptoms⁴. LVAD patients with worsening HF or impaired pump performance due to suboptimal hemodynamics are often re-hospitalized. In the ROADMAP study, about 80% of LVAD patients were re-hospitalized within a year after implant, and 10% of readmissions were due to pressure/volume management or worsening HF⁵.

Improved hemodynamic monitoring of LVAD patients may reduce the readmission burden due to HF and volume management. CardioMEMS is an implantable wireless pressure sensor proven to reduce hospital admissions in NYHA class III patients. In the CHAMPION trial, CardioMEMS provided daily monitoring of PA pressure to optimize drug therapy in HF patients, resulting in a 37% reduction of HF related hospitalizations¹. In addition to reduced readmission rates, HF management with CardioMEMS leads to improved quality of life, NYHA class, and six-minute walk distance^{1,6}. In LVAD patients, remote monitoring with CardioMEMS should allow physicians to intervene earlier when hemodynamic deterioration occurs. Appropriate medication or pump speed changes can be made to optimize pulmonary artery pressure and indirectly left ventricular filling pressure which may reduce HF hospital readmissions⁷. Frequent hemodynamic optimization may lead to improved functional status and quality of life, especially for patients who are failing to respond well to LVAD therapy.

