4.3.1 Descriptive Endpoints

1. Change in Six Minute Hall Walk (6MHW) distance from enrollment to six months
2. Changes in CardioMEMS PA pressure over time
3. Percentage of days PA pressure is in the pre-specified target range
4. Changes in PA pressure before 6MHW test to after 6MHW test
5. Device malfunction (e.g. loss of performance in either device)
6. NYHA classification at baseline and each scheduled follow-up visit
7. Health related quality of life (EQ-5D-5L)
8. All-cause hospitalization rate
9. Heart failure hospitalization rate including emergency department visits, or unscheduled clinic visits for worsening HF, volume management, and/or cardiovascular medication management
10. Change in 6MHWD, NYHA class, health related quality of life, or unscheduled hospitalizations by PA pressure

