4.4 STUDY POPULATION

The intended population for this clinical investigation is comprised of advanced heart failure patients over the age of 18 years who have a CardioMEMS device and a HeartMate LVAD.

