5.5.2 Scheduled Follow-ups

Follow-up schedules are calculated from the time of baseline. Follow-up visits are scheduled at Months 1, 3, and 6 post study enrollment (two devices implanted). Sponsor Representatives will be involved in providing technical support during the Follow-up procedures.

At each visit, the following procedures must be completed:

- Document all changes in cardiovascular medications: ACE inhibitors, ARBs, beta blockers, nitrates, aldosterone antagonists, digoxin and diuretics
- Record vital signs
- NYHA Classification
- Administer EQ 5D 5L survey
- Review and document changes in pump parameters
- Administer 6MHW test per Appendix D
- CardioMEMS PA readings taken before (at rest) 6MHW test and immediately following 6MHW test, ideally within one minute of test completion (Group A and Group B)
- Emergency room visits, hospitalizations and cause for hospitalization documented
- Occurrence of protocol defined AEs (date of adverse event, determination of the seriousness and/or relation to the device, resolution of the adverse event)
- Reoperations/operative procedures pertaining to the two devices under study (HeartMate and, CardioMEMS)
- Pump Replacements/Explants/Device Exchanges (note patients are required to be withdrawn from the study at the time either device is removed)

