6.1 ANALYSIS OF ENDPOINTS

6.1.1 Descriptive Endpoints

The following endpoints will be analyzed using descriptive statistics. Continuous variables will be summarized using numbers of subjects, mean, standard deviation, median, minimum, and maximum. Categorical variables will be summarized using frequency and percentages. Rate data will be summarized using events per patient-time.

1. Change in Six Minute Hall Walk (6MHW) distance will be summarized as change from baseline and using raw values, at 1, 3, and 6 months.
2. Changes in CardioMEMS™ PA pressure over time will include PA systolic, diastolic and mean pressures; heart rate; and cardiac output (calculated using latest algorithm for CardioMEMS) and will be summarized at baseline, throughout the study, and at 6 months.
3. Percentage of days over 6 months that PA diastolic pressure is between 8 and 15 mmHg will be summarized using the total number of days that pressures were measured as the denominator. The percentage will also be calculated at different points during the study. This endpoint will be used to assess the impact of medication and pump speed changes on PA pressures.
4. Changes in PA pressure before the 6MHW test to after the 6MHW test will be summarized at baseline (Group A only) and at 1, 3, and 6 months for both groups.
5. Device malfunction will include all instances of loss of performance of either device and will be summarized separately by device and type of loss of performance at 1, 3, and 6 months.
6. NYHA classification will be analyzed as a categorical variable and as a continuous variable at baseline, 1, 3, and 6 months. Change from baseline in NYHA will be analyzed similarly.
7. Health related quality of life (EQ-5D-5L) total score and visual analogue scale will be scored using the recommended scoring algorithms and analyzed at baseline, 1, 3, and 6 months. The change from baseline in EQ5D-5L will be analyzed similarly.
8. All-cause hospitalization rate will be summarized over 6 months in units of events per patient-time.
9. Heart failure hospitalization rate including emergency department visits, or unscheduled clinic visits for worsening HF, volume management, and/or cardiovascular medication management will be summarized over 6 months in units of events per patient-time.
10. Change in 6MHWD, NYHA class, EQ-5D-5L, or unscheduled hospitalizations will be analyzed descriptively according to subgroups based on PA diastolic pressure.

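### Appendix B does not say that HF must be the principal diagnosis or cause of an HF hospitalization, and endpoint 9 pools these admissions with ED and clinic visits, with no separate HF-admission rate planned

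*Combined protocol and SAP*

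**What the plan says.** Two entries in Appendix B set the definition. Hospitalization is "Defined as an admission to the hospital for greater than or equal to 24 hours". A hospitalization is then "determined to be related to heart failure when the diagnosis of heart failure is listed on the discharge diagnosis". Neither entry mentions a principal diagnosis or the reason for admission.

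The term feeds endpoint 9. Section 6.1.1, item 9, summarizes over 6 months, per patient-time, a "Heart failure hospitalization rate including emergency department visits, or unscheduled clinic visits for worsening HF, volume management, and/or cardiovascular medication management". Section 4.3.1 lists the same endpoint. Endpoint 8 is the all-cause rate, and endpoint 10 looks at unscheduled hospitalizations by PA pressure subgroup. Section 6.1.2 adds nothing on HF admissions.

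On data capture, Section 5.5.2 asks for "Emergency room visits, hospitalizations and cause for hospitalization documented" at each visit, and Section 5.8.3 has all admissions recorded with their reasons. Section 5.8.2 requires HF-related emergency visits and stays under 24 hours to be reported. Section 5.8.1, on unscheduled office visits, asks for reportable adverse events and for medication or pump changes with their reasons. It does not explicitly ask for the reason for the visit.

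**The concern.** Section 4.4 describes the population as "advanced heart failure patients over the age of 18 years who have a CardioMEMS device and a HeartMate LVAD". HF is therefore a standing diagnosis for everyone enrolled and may be listed at discharge after an admission for something else. A definition that turns on a listing may not separate HF admissions from others in this population.

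The study's rationale is stated by cause. Section 2 says "Improved hemodynamic monitoring of LVAD patients may reduce the readmission burden due to HF and volume management", and its benchmark from an earlier LVAD study is that "about 80% of LVAD patients were re-hospitalized within a year after implant, and 10% of readmissions were due to pressure/volume management or worsening HF". A count based on listing does not compare cleanly with that benchmark. It could also err the other way, by missing a volume-management admission on which HF is not listed.

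Pooling adds a second difficulty. A reader of endpoint 9 would see one rate under the name hospitalization, with no way to tell how much of it is admissions. Section 6 says the results will be used to design future trials. An HF-admission rate is a natural input to such a design, and the listed analyses do not produce one.

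**Working it through.** **Text check**

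1. *Definition.* Read literally, any listing of HF is enough. The singular wording, the discharge diagnosis, can also mean the principal one. The text does not decide between them. Cause is collected (Sections 5.5.2 and 5.8.3), but Appendix B does not use it. Section 5.14 names only a Steering Committee and a Publication Committee, and no event adjudication is described.
2. *Endpoint against definition.* Appendix B needs at least 24 hours. ED and clinic visits in endpoint 9 need not last that long, so the endpoint's name does not match the plan's own term. Short stays under 24 hours are collected (Section 5.8.2), but endpoint 9 does not say whether they count.
3. *Other outputs.* Endpoint 8 includes HF admissions without identifying them. Endpoint 10 is not specific to HF. So the only planned HF-specific figure is the pooled one.
4. *Capture.* Admissions have reasons. ED visits related to HF are reported. Reasons for other ED visits and for unscheduled clinic visits are not explicitly requested. Adverse event reporting does not fill the gap, because worsening HF is reportable only if possibly or likely related to study procedures or devices (Section 8.2).

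**Illustration of scale (not an estimate)**

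The plan gives no expected HF rate, and the 100 subjects in Section 6.2 carry no calculation, so there is no figure to reproduce.

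Inputs from the documents: 100 subjects and 6 months (Section 4.1); 80% readmitted within a year and a 10% HF or volume share (Section 2, another study). Assumed: a constant Poisson rate, full follow-up, an alternative share p of 30%, and every value of x, the fraction of other admissions that also list HF.

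- Rate = -ln(1 - 0.80) = 1.61 per patient-year
- Patient-years = 100 × 0.5 = 50
- Admissions = 1.609 × 50 = 80.5
- Counted as HF = 80.5 × (p + (1 - p)x)
- Inflation = (p + (1 - p)x) / p

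| p | x = 0 | x = 0.10 | x = 0.25 | x = 0.50 |
|---|---|---|---|---|
| 0.10 | 8.0 (1.00) | 15.3 (1.90) | 26.2 (3.25) | 44.3 (5.50) |
| 0.30 | 24.1 (1.00) | 29.8 (1.23) | 38.2 (1.58) | 52.3 (2.17) |

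Cells show counted HF admissions, with the inflation factor in brackets. The column x = 0 gives the same count as a principal-diagnosis reading.

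*Pooling.* Take 8 admissions and add an assumed 8, 16, 40 or 80 ED and clinic visits. The endpoint 9 rate becomes 16/50 = 0.32, 24/50 = 0.48, 48/50 = 0.96 or 88/50 = 1.76 per patient-year. Admissions make up 50%, 33%, 17% or 9% of the events.

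*Precision of a cause-based rate.* With 8 events the rate is 8/50 = 0.16 per patient-year (exact Poisson 95% CI 0.07 to 0.32). With 24 events it is 0.48 (0.31 to 0.71). Relative to an any-listing count, the relative standard error grows by the square root of the inflation factor: √1.23 = 1.11 to √5.50 = 2.35 over the table's non-zero x.

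**The case against.** The strongest reply is that little depends on this. Section 6 describes a feasibility study with descriptive endpoints and no formal hypothesis tests, and Section 6.4 sets no success criterion. That stands, and it is why the point is minor.

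Second, endpoint 9 states openly what it includes, and a separate admission rate could be tabulated from data already held. Both are true. The gap is in the definition and the listed outputs, not in the capture of admissions. That makes prespecifying the split cheap, but it does not make the split part of the plan.

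Third, the causal phrase in endpoint 9 might be read as governing the whole list, admissions included. If so, endpoint 9 and Appendix B apply different rules to the same admission, which still needs settling.

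A reader might infer that sites will classify differently, or that the HF-admission rate will be inflated several-fold. The documents support neither. They do not say that each site's own reading decides the matter; sponsor staff review data and source documents (Section 10) and can obtain admission records (Section 8.3). The larger factors in the table come from assumed values of x. The 10% share comes from the year after implant, while these subjects need at least 3 months of support and Group B enters with NYHA class III symptoms and a prior HF hospitalization (Section 4.4.1).

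**Conclusion.** The point holds as one of definition and reporting. Appendix B leaves open whether HF must be the principal diagnosis or cause, in a population where all subjects have HF. Endpoint 9 is named a hospitalization rate but includes visits that need not meet the plan's 24-hour definition, and no separate HF-admission rate is planned. These conclusions rest on the text alone.

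The size of any distortion is unknown. It is nil under a principal-diagnosis reading. Under a literal reading it depends on how often HF is listed after other admissions, which the documents do not give. They also give no ED or clinic-visit frequency, so no figure can be put on endpoint 9 as a whole. Severity is minor: no test, success criterion or other endpoint depends on the HF definition. It is still worth correcting, because descriptive rates are what this study hands to the design of later trials.

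**What to change.** 1. **Definition for endpoint 9.** Count an admission of at least 24 hours as an HF hospitalization only when worsening HF is the principal discharge diagnosis or the primary recorded reason for admission. Give admissions for volume or cardiovascular medication management their own row, and state whether that row enters the composite. Do not count low-volume events as HF hospitalizations: Appendix F treats low pressure as volume depletion, and Section 8.2 lists hypovolemia among possible effects of managing to target. State that this endpoint definition leaves the Group B eligibility wording in Section 4.4.1 unchanged.
2. **Reporting.** In Sections 4.3.1 and 6.1.1, item 9, keep the composite and label it HF events. Beside it, give rates per patient-time for (a) HF hospitalizations, (b) HF-related ED visits and short stays under 24 hours, and (c) unscheduled clinic visits for the reasons endpoint 9 names. Count a visit that leads to admission once, as an admission.
3. **Capture.** Confirm that the CRFs record the reason for ED visits not labelled HF-related and for unscheduled clinic visits. If they do not, add the field or report those components as incompletely captured.

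*Cost.* Wording in three places, a few table rows and possibly one CRF field. Section 5.8.3 speaks of reasons in the plural, so sites must mark one as primary. The HF-admission rate will rest on fewer events than an any-listing count and be less precise. Clinical management is unaffected.
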